## **8.2. Statistical Methods**

Descriptive statistics will be used to describe the collected variables: mean and standard deviation, median and interquartile range for quantitative variables, and absolute frequencies and percentages for qualitative variables. The comparison between the proportion of subjects making an informed choice in the two groups will be evaluated using the Chi-square test, as will the comparison between the proportion of subjects adhering to screening in the two arms.

Median scores obtained from the knowledge questionnaire will be evaluated using the Friedman test at the three time points.

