### 6.1. Intervention Procedures

All subjects who meet the inclusion criteria will receive, through an attachment to the invitation letter (Annex 1) for screening, the instructions on how to download the application on their smartphone. Once downloaded, the application will allow exclusively to complete the informed consent (Annex 2), to read the privacy policy (Annex 3) and subsequently the baseline questionnaire (T0) (Annex 4), in digital format. Afterwards, the users will be progressively randomized into an intervention arm and a control arm. Recruitment will be stopped upon enrollment of subject number 2500.

Subjects assigned to the control arm will have access to the mobile application in a limited version. In a specific section, there will be standardized and digitalized scientific dissemination documents aimed at providing information on primary prevention, healthy and correct lifestyles, and on colorectal cancer screening.

Subjects assigned to the intervention arm will have access to the full version of the application. In particular, in addition to the specific section available for the control group, users will be presented with the aforementioned information in the form of daily “pills.” Moreover, by completing one quiz per week and one twice a week, the user will be able to earn points based on the number of correct answers provided. The quizzes will be of two types: the first, weekly, will consist of 10 questions, 5 regarding primary prevention topics and 5 on general knowledge; the second, every 3 days, will consist of 3 prevention-related questions. Users will have 15 seconds to answer each question, and the score, in case of a correct answer, will be assigned based on the time taken to select it.

For both arms, it will be possible to fill in a follow-up questionnaire at T1 and T2 (Annex 5), respectively at 3 and 6 months from enrollment.

The project foresees a total duration of 30 months.

It is possible to identify three main phases:

**Phase 1**, called **Project Start-Up**, consists of:

- 1.1 Drafting of the Study Protocol
- 1.2 Design of the CRF, creation of the electronic database and related completion manual
- 1.3 Definition of the Statistical Analysis Plan (SAP)
- 1.4 Preparation and submission of the documentation to the relevant Ethics Committee

**Phase 2**, called **Study Set-Up**, includes:

- 2.1 Identification of the cohort, patient enrollment and randomization

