3.1 Data analysis and dissemination of results (publications and conference materials)

## 6.2. Data Collection Tool

Two digital questionnaires (to be completed directly within the App) will be used: one at time T0 (baseline) and the second at time T1 (three months) and T2 (six months). In particular:

1. Within the questionnaire administered at baseline, the validated Multidimensional Health Locus of Control (MHLC) questionnaire is included. It contains eighteen questions through which the Locus of Control of the participants will be assessed.
2. Informed choice will be evaluated through three items: knowledge (score of at least 7 out of 13), attitude (score > 24), and intention (actual behaviour). Among these, the first two items must necessarily be satisfied in order to define that the subject is informed about the choice.
3. The level of knowledge related to healthy behaviours and primary prevention will be assessed through the 13 questions on primary prevention and healthy lifestyle behaviours. Based on the number of correct answers, subjects will be classified into three categories: low knowledge (0 to 5 out of 13), good knowledge (6 to 8 out of 13), and excellent knowledge (9 to 13 out of 13).
4. Decision conflict, customer satisfaction, and the acceptability of the App will be assessed at T1 and T2 through specific items of the second questionnaire (decision-making process, satisfaction, and decision-aid acceptability).

In addition, Brescia LHA will provide data on residents born in 1973 and 1974, by sex, and the number of subjects, by sex, who actually completed the FOBT screening.

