## 7. Study Duration and Planned Assessments

The duration of the study will be 30 months. The enrollment period will take place from January 2023 to August 2024, in conjunction with the invitation sent by Brescia LHA to citizens born in 1973 and 1974 to undergo FOBT screening. Following the completion of the informed consent and the baseline questionnaire, users will be progressively randomized.

The total enrolment period will last 20 months. Assessments for each subject will be performed at baseline (T0), at 3 months (T1), and at 6 months (T2).

**T0:** questionnaire collecting information on socio-demographic data, risk perception, knowledge, attitude, intention, and Locus of Control.

**T1:** questionnaire collecting information on risk perception, knowledge, attitude, intention, decision-making process, customer satisfaction, and application acceptability.

**T2:** same questionnaire administered at T1.

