## 8. Statistical Aspects

### 8.1. Sample size

Based on previous studies, we considered an absolute difference of 10% between the proportion of individuals who make an informed choice and those who do not to be the minimum important difference for the sample size calculation. Assuming that the proportion of individuals making an informed choice is 50%, with a power of 90% and a two-sided significance level of 5%, 519 subjects per group are required, for a total of 1,038 subjects.

Considering an estimated colorectal cancer screening adherence rate of 50% in the province of Brescia and a probable drop-out rate of 20%, at least 2,492 subjects will need to participate in the study.

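### The primary chi-square ignores pre-randomisation T0 knowledge, attitude and intention and names no visit; a baseline-adjusted analysis at one named visit could be more precise at almost no cost.

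*Combined protocol and SAP*

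**What the plan says.** Section 8.2 (Statistical Methods) sets the primary analysis: "The comparison between the proportion of subjects making an informed choice in the two groups will be evaluated using the Chi-square test". It mentions no covariate and no time point. The only analysis that uses the repeated visits is a Friedman test, and that concerns knowledge scores, not informed choice.

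Section 7 fixes the order of events: "Following the completion of the informed consent and the baseline questionnaire, users will be progressively randomized". It describes T0 as a "questionnaire collecting information on socio-demographic data, risk perception, knowledge, attitude, intention, and Locus of Control". Section 6.1 gives the same order and adds that for both arms "it will be possible to fill in a follow-up questionnaire at T1 and T2", at 3 and 6 months. Section 4 specifies simple randomisation and no stratification.

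Section 6.2 defines informed choice by "knowledge (score of at least 7 out of 13), attitude (score > 24), and intention (actual behaviour"), the first two being mandatory. Sections 3.1, 6.2, 8.1 and 8.2 do not say whether this is judged at T1 or T2.

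Section 8.1 sizes the trial on an absolute 10-point difference from 50%, "with a power of 90% and a two-sided significance level of 5" per cent, giving 519 per group. It then inflates the total for 50% screening adherence and 20% drop-out. Section 6.1 caps enrolment: "Recruitment will be stopped upon enrollment of subject number 2500".

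**The concern.** The primary endpoint is built mainly from thresholds on knowledge and attitude scores. The same constructs are measured before allocation, and completing T0 is a step before randomisation, so these covariates should exist for everyone randomised. They are likely to be among the best available predictors of the endpoint, and the primary test does not use them. Because randomisation is simple, neither the design nor the analysis deals with chance imbalance in T0 knowledge or attitude. The interval around the primary difference may therefore be wider than the collected data allow.

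The second gap is the visit. With the questionnaire given at both T1 and T2, there are two candidate primary results and no rule for choosing between them, so the choice could be made after the data are seen.

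A related ambiguity is that section 6.2 equates intention with actual behaviour. If that means FOBT uptake, T0 can hold only stated intention. The outcome being modelled should be settled before the model is written down.

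**Working it through.** **1. The plan's own figure.** Two proportions, 0.50 and 0.60, two-sided 5%, power 90%, pooled variance under the null, no continuity correction:

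n = [1.960 × √(2 × 0.55 × 0.45) + 1.2816 × √(0.50 × 0.50 + 0.60 × 0.40)]² / 0.10² = [1.379 + 0.897]² / 0.01 = 518.04, rounded up to 519 per arm.

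This reproduces section 8.1 exactly, so the sizing takes no credit for baseline data.

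**2. How many will be evaluable.** Section 8.1 applies both losses, but it is unclear whether non-adherers drop out of the primary analysis. Starting from the cap of 2,500:

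- Reading A (both losses): 2,500 × 0.50 × 0.80 / 2 = 500 per arm.
- Reading B (drop-out only): 2,500 × 0.80 / 2 = 1,000 per arm.

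Unadjusted power = Φ{[0.10 × √n − 1.960 × √0.495] / √0.49}, which gives 90.1% at 519, 89.0% at 500 and 99.5% at 1,000 per arm.

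**3. Variance explained by T0 (assumed correlations).** T0 and follow-up knowledge and attitude were drawn as normal scores (N = 1,000,000), with knowledge and attitude independent. The endpoint was both follow-up scores above threshold, with thresholds set to give 50% and 60%. A logistic model on the T0 scores gave the share of variance explained, R. The intention item was not modelled.

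**4. Effect on power and interval.** Multiply the variance by (1 − R), which is the same as replacing n by n/(1 − R). The 95% half-width is 1.96 × √[0.49 × (1 − R)/n].

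| T0-to-follow-up correlation | R | Power, 500/arm | Half-width, 500/arm | Power, 1,000/arm | Half-width, 1,000/arm |
|---|---|---|---|---|---|
| none (chi-square) | 0 | 89.0% | 6.1 points | 99.5% | 4.34 points |
| 0.1 | 0.5% | 89.1% | 6.1 | 99.5% | 4.33 |
| 0.3 | 4.1% | 90.2% | 6.0 | 99.6% | 4.25 |
| 0.5 | 11.7% | 92.4% | 5.8 | 99.8% | 4.08 |
| 0.7 | 23.3% | 95.3% | 5.4 | 99.9% | 3.80 |

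If knowledge and attitude are themselves correlated at 0.3, R is 0.5, 4.8, 13.3 and 26.6%, and power at 500 per arm is 89.1, 90.4, 92.8 and 96.1%.

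**5. Simulation checks of the adjusted analysis.**

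- 10,000 trials of 500 per arm, knowledge-attitude correlation 0.3, T0-to-follow-up correlation 0.3, 0.5 and 0.7: unadjusted power 89.4%; power of the standardised risk difference 90.7, 92.6 and 95.7%; variance ratio to unadjusted 0.955, 0.874 and 0.745; type I error 5.0, 5.5 and 4.9%.
- 3,000 trials of 519 per arm with three baseline covariates: if the covariates predict nothing, the variance ratio is 1.002 and power is 89.5% against 89.4%. Under the null with R about 0.17, type I error is 4.6% against 4.5% for the chi-square.
- The gain does not appear as a smaller standard error for the odds ratio. At R about 0.17 the log odds ratio rises from 0.408 to 0.495 and its standard error from 0.126 to 0.139. The precision gain shows on the risk-difference scale.

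**6. Two visits.** The plan does not say that both will be tested as primary. If both were tested at 5% and either counted as success, P(|Z₁| > 1.96 or |Z₂| > 1.96) under a bivariate normal is 9.1, 7.8 and 7.0% at assumed T1–T2 correlations of 0.5, 0.8 and 0.9.

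**The case against.** An unadjusted comparison of two proportions in a simply randomised trial is a legitimate pre-specified choice. It agrees with the sample-size calculation, and nothing in the documents contradicts it. The gain rests entirely on assumed correlations: at 0.1 to 0.3, power at 500 per arm moves by about one point or less, and at 1,000 per arm power needs no help. The model is also favourable. It uses continuous scores where knowledge has 13 items, and the same T0-to-follow-up correlation in both arms, although the full app is meant to change knowledge and may weaken that correlation in the intervention arm. The two-visit error rates describe a plan that nobody wrote. One simulated type I error, 5.5%, lies about 2.3 Monte Carlo standard errors above 5%.

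Most of this stands as a limit on size. The benefit could be small, and adjustment is a recommendation, not the repair of an invalid test. It does not remove the point. With assumed correlations of 0.5 in control and 0.2 in intervention, the share explained is still about 6%, and power at 500 per arm is 90.7%. The other simulated type I errors, 5.0, 4.9 and 4.6%, show no pattern of inflation. T0 scores are legitimate covariates whichever way the third component is read, so that ambiguity bears on the outcome, not on whether adjustment is allowed. None of the objections supplies the missing primary visit.

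**Conclusion.** The point holds, as an inexpensive improvement and not as a flaw that invalidates the trial. The chi-square is unbiased and correctly sized. It discards baseline information that the trial already collects, and the loss ranges from negligible (0.5% of variance at a correlation of 0.1) to material (23% at 0.7). The documents do not allow a narrower estimate. If both losses in section 8.1 occur, the cap of 2,500 leaves about 500 per arm, just short of 519, and a correlation of 0.3 is enough to bring power back above 90%. If only drop-out applies, the gain is an interval narrower by at most 4.34 − 3.80 = 0.54 points over the range examined. If the T0 measures predict nothing, the cost in precision is negligible.

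The absence of a named visit does not depend on any assumption: as written, the primary test is not fully specified. The 7.0 to 9.1% error rates apply only if both visits were tested and either counted.

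**What to change.** In section 8.2 or the SAP, before any comparison of follow-up data by arm:

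1. State whether the third component of informed choice is stated intention or actual FOBT uptake. If uptake, say how it will be obtained per participant; sections 6.2 and 10 describe the health authority's data only as counts by sex.
2. Name T1 or T2 as the primary visit, tested at two-sided 5%, and make the other secondary.
3. Make the primary analysis a logistic model at that visit with arm, T0 knowledge score, T0 attitude score and T0 stated intention, their form fixed in advance.
4. Report the standardised risk difference with a 95% CI, and state how the interval is computed. This keeps the absolute 10-point scale of section 8.1.
5. Keep the chi-square as a supportive analysis. The primary contrast needs no repeated-measures model.

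The cost is a few sentences and a little programming. All covariates are already collected at T0, and the sample size does not change.

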## **2.2. Secondary Objectives**

1. To assess and compare screening adherence rates between the two study arms.
2. To assess and compare, between the two study arms, the level of knowledge related to healthy behaviours and primary prevention.
3. In the intervention arm, to evaluate decision conflict, customer satisfaction, and the acceptability of the mobile application.

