### **3.2. Secondary Endpoint**

1. Screening adherence rate, calculated as the ratio between the number of individuals who completed the screening and the total number of individuals invited to participate in the screening program in the two study arms.
2. Level of knowledge related to healthy behaviors and primary prevention in the two study arms will be measured using a digital questionnaire containing 13 questions on primary prevention and healthy lifestyle behaviors.
3. Decision conflict, customer satisfaction, and the acceptability of the application will be assessed through additional questions included in the same digital questionnaire.

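### Secondary objective 2 compares knowledge between arms, but the only test named for knowledge is a Friedman test over time, which has no arm term

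*Combined protocol and SAP*

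**What the plan says.** Section 2.2 states the second secondary objective as follows: "To assess and compare, between the two study arms, the level of knowledge related to healthy behaviours and primary prevention". Section 3.2 defines the matching endpoint as "Level of knowledge related to healthy behaviors and primary prevention in the two study arms", measured with 13 questions. Section 6.2 turns the number of correct answers into levels: "subjects will be classified into three categories: low knowledge (0 to 5 out of 13), good knowledge (6 to 8 out of 13"), with 9 to 13 as the top level.

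Section 8.2 is the only statistical-methods text in the combined document. It names a between-arm Chi-square test for informed choice and another for screening adherence. For knowledge it gives one sentence: "Median scores obtained from the knowledge questionnaire will be evaluated using the Friedman test at the three time points". It also says that "Descriptive statistics will be used to describe the collected variables".

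Two details of measurement are open. In its item on informed choice, section 6.2 uses "knowledge (score of at least 7 out of 13"), and a separate item describes the 13 primary-prevention questions. Section 8.2 does not say which of these is the knowledge questionnaire. Section 7 describes T0 as a "questionnaire collecting information on socio-demographic data, risk perception, knowledge, attitude, intention, and Locus of Control", without saying which knowledge items are included.

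**The concern.** The objective asks whether the arms differ. The planned test asks whether scores change between T0, T1 and T2. If it is run on all participants together, it ignores randomisation. If it is run in each arm, it gives two p-values, and finding one significant and the other not is not a test of the difference between arms.

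The distinction matters in this trial because the control arm also receives digital material on prevention, lifestyle and screening (section 6.1). Both arms may well improve, and a significant Friedman result could then be read as an effect of the full app. Section 8.2 names no between-arm test, effect estimate with confidence interval, or comparison visit, either for the 0–13 score or for the three levels. The choice between score and levels, and between T1 and T2, would be left until the data are in.

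**Working it through.** **Objectives against tests**

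| Between-arm outcome | Between-arm test in section 8.2 |
|---|---|
| Informed choice (primary) | Chi-square |
| Screening adherence (secondary 1) | Chi-square |
| Knowledge (secondary 2) | None; Friedman over T0, T1, T2 only |

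The gap follows from this table alone. The simulations below only illustrate its consequences.

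**Sample size.** The plan has no figure for knowledge, so I take 519 per arm from section 8.1 ("519 subjects per group are required, for a total of 1,038 subjects"). It reproduces for 50% against 60%, 90% power and two-sided 5%:

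n = [1.960·√(2·0.55·0.45) + 1.282·√(0.5·0.5 + 0.6·0.4)]² / 0.10² = (1.379 + 0.897)² / 0.01 ≈ 518.0, rounded up to 519.

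**Assumptions, not in the documents.** Baseline mean 7, SD 2.5 and correlation 0.5 between visits. Each person has three equicorrelated normal scores, rounded and limited to 0–13, and the gain is present at both T1 and T2. The Friedman test is tie-corrected. The comparator is ANCOVA at T2 adjusted for T0. Tests are two-sided at 5%, with 8,000 simulated trials per row.

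| Gain in items, one arm / other arm | Pooled Friedman significant | Friedman significant in exactly one arm | ANCOVA significant |
|---|---|---|---|
| 0 / 0 | 4.8% | 9% | 4.9% |
| 0.1 / 0.1 | 20.2% | 22% | 5.3% |
| 0.2 / 0.2 | 64.5% | 47% | 5.2% |
| 0.3 / 0.3 | 95.3% | 42% | 5.3% |
| 0.5 / 0.5 | 100% | 2% | 5.1% |
| −0.25 / +0.25 | 5.3% | 50% | 95.7% |
| 0.1 / 0.6 | 98.8% | 88% | 95.5% |

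In the first five rows the arms do not differ. ANCOVA stays near 5%, while the pooled Friedman rate climbs with the common gain.

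**Checks by hand**

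- Exactly one arm significant at 0.2 / 0.2: the per-arm rates are 0.36 and 0.35, so 0.36·0.65 + 0.35·0.64 = 0.458, close to the simulated 47%.
- ANCOVA precision: SE = 2.5·√(1 − 0.5²)·√(2/519) = 2.165·0.0621 = 0.134. The 95% half-width is 1.96·0.134 = 0.26 items.
- ANCOVA power for a 0.5-item difference: 0.5/0.134 − 1.96 = 1.77, so about 96%.

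**Sensitivity.** Mean 6–9, SD 2.1–2.5, correlation 0.3–0.7 and 400–1,000 per arm were varied one at a time (1,500 runs per cell):

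- Pooled Friedman at 0.2 / 0.2: 49% to 91%.
- Exactly one arm significant at 0.2 / 0.2: 38% to 52%.
- At −0.25 / +0.25: pooled Friedman 4% to 6%, ANCOVA 88% to 100%.

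**A different model.** With 13-item binomial scores (person SD 0.6 on the logit scale, 519 per arm, 400 runs), equal improvement of 0.3 logit gave pooled Friedman 100% and a between-arm rank-sum test at T1 5%. Arms diverging by ±0.15 logit gave 4.5% and 100%.

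**The case against.** No between-arm test of knowledge was found elsewhere in the document. The serious objections concern the illustration and the scope.

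- **519 may be the wrong number.** Section 8.1 inflates for 50% screening adherence, but a questionnaire score does not depend on having had the FOBT. With only the 20% drop-out applied, 2,492 × 0.8 / 2 ≈ 997 per arm would have knowledge data. This stands, but it makes the problem larger: at 1,000 per arm the pooled Friedman rate for equal 0.2 gains is about 91%.
- **The opposite-direction case is extreme.** It needs one arm to lose knowledge although both receive information. This stands. In the more natural 0.1 / 0.6 case the pooled Friedman test rejects in 98.8%. That rejection still says nothing about the arms, since equal gains of 0.3 give 95.3%.
- **One-at-a-time ranges are narrow.** This stands too. Varied together, the rate at 0.2 / 0.2 runs from 41% to 100%.
- **Knowledge is already tested through informed choice.** It enters there only as a component cut at 7 of 13 and combined with attitude and intention. That tests the composite, not the level of knowledge.
- **The two 13-point measures may be one scale.** The documents do not settle this. If they are one, the named test addresses the wrong contrast. If they are two, the Friedman test may concern the other scale, and objective 2 then has no named test at all. Neither reading supplies a between-arm comparison.
- **Section 6.1 lists defining a SAP as a project step.** The combined document contains no analysis text beyond section 8.2, so the step does not close the gap.

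**Conclusion.** The concern holds. Followed as written, section 8.2 yields descriptive figures for objective 2 and a p-value that answers a different question. This is certain from the form of the test and needs no assumed value.

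The size is illustrative. With no app effect and a common gain of 0.2 items, the planned test, if pooled, is significant in roughly two trials in three under the base assumptions, and nearer nine in ten with about 1,000 per arm. Run by arm, it gives a false appearance of a difference in about 47% of trials at 519 per arm. The percentages depend on the assumed mean, SD, correlation and gains.

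One secondary objective is affected; the primary endpoint and the sample size are not. It should be fixed before the analysis, but it does not threaten the trial's main conclusion.

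**What to change.** Amend section 8.2 as follows.

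1. State that the scale is the 13 primary-prevention questions, and confirm whether they are asked at T0.
2. Fix one comparison visit in advance, for example T2 with T1 as supporting.
3. Name one main between-arm analysis. ANCOVA of the 0–13 score adjusted for T0, reported as an arm difference with 95% CI, is the natural choice. The three levels can be compared at the same visit by ordinal regression adjusted for T0 or, in the style of the present text, by a Mann-Whitney or Chi-square test. Say which analysis is the main one.
4. If the items are not asked at T0, use the unadjusted between-arm comparison.
5. Keep the Friedman test as a within-arm description only.

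Any of these between-arm analyses closes the gap. For an assumed 0.5-item difference with 519 per arm, power is about 96% for ANCOVA, 89% for adjusted ordinal regression, 83% for Mann-Whitney on the levels and 74% for Chi-square on the levels. With about 1,000 per arm these differences largely disappear, so the choice among them matters less than making it in advance.

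The cost is a few sentences in section 8.2 and a few lines of code. No new data and no change in sample size are needed.

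### The only test planned for knowledge scores, the Friedman test, leaves out everyone who missed T1 or T2, although follow-up is optional and 20% drop-out is expected

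*Combined protocol and SAP*

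**What the plan says.** Section 8.2 plans descriptive statistics for the collected variables, chi-square tests for informed choice and for screening adherence, and one method for knowledge: "Median scores obtained from the knowledge questionnaire will be evaluated using the Friedman test at the three time points". The statistical section defines no analysis population, no rule for unreturned questionnaires, no imputation and no sensitivity analysis.

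Baseline is complete by design, because section 7 places it before allocation: "Following the completion of the informed consent and the baseline questionnaire, users will be progressively randomized". Follow-up is different. Section 6.1 says "For both arms, it will be possible to fill in a follow-up questionnaire at T1 and T2", which makes it voluntary, and section 6.2 has participants answer inside the application: "Two digital questionnaires (to be completed directly within the App) will be used". Section 8.1 allows for "a probable drop-out rate of 20" per cent, without saying whether this applies to each visit or to the whole six months.

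Secondary objective 2 (section 2.2) is to compare knowledge between the two arms.

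**The concern.** The Friedman test treats each participant as a block and ranks T0, T1 and T2 within it. A block with an empty cell cannot be ranked. A standard implementation (scipy) given one missing cell returns no result, and runs only once that participant is omitted. A person who answered T0 and T1 but not T2 therefore contributes nothing to the test.

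Two things are at stake. First, returned questionnaires go unused in the only inferential analysis of this endpoint. Second, the people left are those who came back to the application at both 3 and 6 months. If coming back goes with learning more, the change seen in them is larger than in everyone randomised. Only the intervention arm receives daily content and scored quizzes, so this selection could differ by arm. The test also gives no estimate of the size of the change.

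**Working it through.** **The plan's own figure.** The documents give no sample size or power for knowledge, only for informed choice. For 50% against 60%, two-sided 5%, 90% power and pooled variance:

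n = [1.960 × √(2 × 0.55 × 0.45) + 1.2816 × √(0.50 × 0.50 + 0.60 × 0.40)]² / 0.10² = (1.379 + 0.897)² / 0.01 ≈ 518.0, rounded up to 519 per group, 1,038 in total.

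Then 1,038 × 1.2 = 1,245.6, rounded up to 1,246, and 1,246 / 0.5 = 2,492. Both figures reproduce. They matter here only as the source of the 20%.

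**Inputs for the counts.** 2,500 enrolled (section 6.1); T0 complete (section 7); 20% drop-out (section 8.1). The pattern of missing visits is an assumption, because the documents do not give one. Let m1 and m2 be the proportions missing T1 and T2.

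- *Cumulative and monotone, 20% gone by T2.* Complete: 2,500 × 0.80 = 2,000. Returned T1 unused: 2,500 × (0.20 − m1), which is 500 if nobody leaves before T1, 250 if 10% do, and 0 if all 20% do.
- *Independent, 20% at each visit.* Complete: 2,500 × 0.8 × 0.8 = 1,600. Exactly one follow-up, unused: 2,500 × 2 × 0.2 × 0.8 = 800. None: 2,500 × 0.2 × 0.2 = 100. Of 2 × 2,500 × 0.8 = 4,000 returned follow-ups, 800 (20%) are unused.
- *Independent, 10% at T1 and 20% at T2.* Complete: 2,500 × 0.9 × 0.8 = 1,800. One follow-up, unused: 2,500 × (0.1 × 0.8 + 0.2 × 0.9) = 650. None: 50.
- *20% at each visit, never the same people.* Complete: 2,500 × (1 − 0.4) = 1,500. One follow-up, unused: 1,000.

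**Illustration of bias (all inputs assumed).** 400,000 simulated people; a standard normal engagement variable; return at each visit logistic in engagement (log-odds 1 per SD, mean return 80%); true mean gain 1.0 point, SD 1.5, the same at T1 and T2; baseline SD 2 for the model fits. About 66% have complete triplets.

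| Correlation of gain with engagement | Mean gain, complete triplets | Random-intercept model, all returned scores |
|---|---|---|
| 0.3 | 1.14 | 1.04 to 1.08 |
| 0.5 | 1.23 to 1.24 | 1.08 to 1.11 |

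With zero correlation the complete-triplet gain is unbiased. The ranges in the last column reflect different assumed residual errors and baseline-engagement correlations.

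**The case against.** Several points on the other side stand.

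- A reader might infer that the plan discards returned scores altogether. It does not. The descriptive statistics in section 8.2 are not limited to complete triplets, so every returned score can be summarised at its visit. Only the test drops incomplete blocks.
- A reader might infer that the test describes the most engaged users. The documents give no return rates or predictors of return, and in the 20% scenarios 60% to 80% of participants remain. People who completed every wave, probably the more engaged, is as far as the text allows.
- A reader might take 36% incomplete triplets as the plan's expectation. Section 8.1 gives a single 20%, which may be cumulative. If everyone who leaves does so before T1, no returned follow-up is lost.
- The Friedman test reports no gain, so there is no overstated estimate in the plan as such. The 14% to 24% applies to a mean gain computed in the same complete cases.
- Lost precision matters little for detecting change over time. With the assumed gain, 1,600 triplets give z = 1.0 / (1.5 / √1,600) ≈ 27.
- The Friedman test has no arm term and so cannot answer secondary objective 2. That is a separate and more serious gap, and correcting it with a longitudinal model would also resolve this point.

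None of this removes the complete-block requirement, which is a property of the named test and which nothing in the documents offsets.

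**Conclusion.** The point holds in a limited form. As written, the only inferential analysis of knowledge excludes every participant who missed T1 or T2. That leaves about 2,000 of 2,500 if the 20% is cumulative, or about 1,600 if it applies independently at each visit; 0 to 500 returned T1 questionnaires, or 800 people's single follow-up, then go unused. The counts rest on the plan's 20% and an assumed pattern.

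The direction and size of any bias rest wholly on assumed links between engagement, return and gain. It is zero if return is unrelated to gain, and about 14% to 24% upward in a complete-case mean gain in the illustration. It would also go too far to say that a mixed model cures this. In the same illustration it leaves about 4% to 9%, and up to about 11% under some assumptions, because return there depends on engagement that the model does not see.

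This is a cheap and worthwhile improvement to a secondary endpoint. It does not affect the primary analysis.

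**What to change.** In section 8.2:

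1. Make the main knowledge analysis a linear mixed model on all returned T0, T1 and T2 scores, with arm, visit and arm-by-visit fixed effects and a participant random intercept. The arm-by-visit term is needed so that the model serves secondary objective 2; visit and arm alone would assume the same change in both arms.
2. Report the mean change from T0 in each arm and the between-arm difference at T1 and T2, each with a 95% confidence interval.
3. Tabulate questionnaire return by arm and visit.
4. Add a simple missing-not-at-random sensitivity analysis, for example shifting the unreturned scores by a stated range of values in each arm.
5. Keep the Friedman test on complete triplets as a secondary check.

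The cost is a few sentences in the plan and one standard model, with no new data and no further contact with participants. There are two downsides. The model uses a normal approximation for a score bounded at 0 and 13, which is minor at this sample size and is cross-checked by the Friedman test. It also assumes that scores are missing at random, which item 4 is there to probe. Both should be stated in the plan.
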